5.1. Disposition

Subjects in the analysis sets (FAS, PPS, and SS) and within each of the stratification factors, namely statin use and country, will be presented. Subject disposition (analyses of randomized, treated, discontinued with primary reason for discontinuation) for FAS will be summarized using frequency and percentage by treatment group.

Subjects are free to discontinue participation in the study at any time. A subject's participation may also be discontinued at any time at the discretion of the Investigator. Withdrawn subjects will not be replaced.

Per protocol, discontinuation of study drug should not result in discontinuation of study participation. The frequency and percentage of randomized subjects who were not treated, who discontinued study drug, and who terminated the study early by reason will be summarized. Such subjects will be still included in the study analysis and final vital status will be ascertained if at all possible using recognized methods.

A subject's participation in the study will be discontinued if any of the following applies:

- Adverse Event
- Withdrawn Consent
- Abnormal Lab Value
- Lost to Follow-up
- Protocol Violation
- Death
- Other

Possible reasons for discontinuation of study drug and discontinuation of study include consent withdrawal, AEs, lost to follow-up or safety labs.

Disposition data, inclusion and exclusion criteria, subject eligibility, as well information on stratification will be displayed.

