6.10.3 Subject Withdrawal / Discontinuation from Study

Subjects are free to discontinue participation in the study at any time. A subject's participation may also be discontinued at any time at the discretion of the Investigator. Withdrawn subjects will not be replaced. However, discontinuation of study drug should not result in discontinuation of study participation.

A subject's participation in the study will be discontinued if any of the following applies:

- Withdrawal of informed consent
- Subject experiences AEs sufficiently severe to contraindicate continuing the study
- Subject's general condition, in the opinion of the Investigator, contraindicates continuing in the study
- Subject refuses to cooperate; or
- Sponsor elects to end the study, or any portion thereof, for any reason

When a subject decides to discontinue participation in the study, or is lost to follow-up (those subjects whose status is unclear because they fail to appear for study visits without stating an intention to withdraw), a reasonable attempt will be made to contact the subject about the reasons for discontinuation and any AEs. All AEs will be followed until resolved or a stable condition has been established. Subjects withdrawn due to an AE or abnormal laboratory test will be followed until the AE or abnormal laboratory

	Screen	Treatment
--	---------------	------------------

test resolves, or there is an adequate explanation that the AE or abnormal laboratory test was not related to study drug.

For subjects who are lost to follow-up, the Investigator should show “due diligence” by documenting in the source documents the steps taken to contact the subject.

Should a subject request to be withdrawn from the study, the following options should be offered to him/her regarding continued participation:

1. Continued study site visits and procedures following the visit schedule, without medication being dispensed.
2. Telephone (or other communication) contact at regular scheduled study visits. Last visit on treatment and follow-up visit would be at clinic, if at all possible. Concomitant medications, updated contact information, and SAE assessments should be collected at each telephone visit.

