3.4. Study Drug Interruption/Discontinuation

Treatment may be interrupted or discontinued at the discretion of the Investigator and Sponsor, based on AEs, other clinical laboratory data, vital signs measurements, and/or electrocardiogram (ECG) findings.

Subjects discontinuing study drug will continue participation in the study and will complete all remaining study visits. Discontinuation of assigned study drug (RVX000222 or placebo) or high intensity statin therapy should not result in study discontinuation.

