Subjects are uniquely identified by a concatenation of study center number and subject number. All data available from the eCRFs along with some derived variables will be listed. For relevant dates, the actual day relative to start of double-blind treatment will also be listed. Dates will be presented in the format of “DDMMYYYY”.

4.2. Sample Size Justification:

The study design will provide approximately 80% power to declare superiority of RVX000222 arm over Placebo with a hazard ratio of 0.7, a true hazard ratio of 1.0 and at an overall 2-sided 5% significance level.

To calculate the sample size (number of subjects), the following additional information was assumed:

- Total number of narrowly defined MACE events needed: 250
- 10.5% event rate in the placebo arm at 18 months
- 30% relative risk reduction (7.47% event rate at 18 months in the RVX000222 arm)
- Accrual period of 1.7 years (20 months) and a total study duration (including follow-up) of 2.75 years (143 weeks)
- A cumulative drop-out rate of 10% per arm by the end of the study (5% drop out rate per arm by year one)

With the above design and assumptions, a sample size of approximately 2400 randomized subjects enrolled uniformly over 1.7 years with total study duration of 143 weeks and subjects followed until failure, drop out or end of study is estimated to provide the 250 events needed.

The power and sample size for this study was calculated using East 6.2.

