8.2. Primary Analysis

The primary analysis will be a time-to-event analysis. The distributions of the primary endpoint within the RVX000222 and placebo groups will be compared using a two-sided stratified log-rank test (LRT) with an $\alpha = 0.05$ level of significance (two sided). Time to first narrowly defined MACE, defined as a single composite endpoint of CV Death or Non-fatal MI or Stroke, will be calculated using randomization date and date of the confirmed event, or date of last contact for censored subjects. For the purpose of the primary analysis and all subsequent analyses involving CV deaths, events within the undetermined cause of death category will be considered CV deaths. All subjects will be followed until drop-out, death, or study closure. Drop-out may be due to withdrawal of consent from further data collection or lost to follow-up. Subjects who drop-out or are alive at study closure will have their event times censored at the time of last contact.

The primary efficacy analysis will be performed on the FAS. The number and percentage of subjects who experienced the narrowly defined MACE, median survival time and corresponding 95% confidence intervals (CIs) will be tabulated and presented by treatment group. A stratified log-rank test and corresponding test statistic, stratifying by country of enrollment and prescribed statin therapy (atorvastatin or rosuvastatin), at a two-sided α level of 0.05, will be used to compare the survival rate between the two treatment groups. If stratifying by country results in too many empty cells, stratifying by geographic region may be considered.

As supportive analyses, the primary efficacy analysis will be

1. repeated for the PPS set
2. repeated for FAS set but using just events adjudicated as CV deaths excluding “undetermined cause of death events”. This analysis will be outside the analysis hierarchy of the study and will not influence secondary endpoint analyses.
3. performed on the FAS using an unstratified LRT as a supportive analysis.

Kaplan-Meier plots for the primary and key secondary endpoints by treatment groups will be presented. Presentation of primary analyses will include estimated hazard ratios and associated 2-sided CI obtained from Cox Proportional Hazard (CPH) models with treatment as the single factor, stratified by country of enrollment and prescribed statin therapy (atorvastatin or rosuvastatin).

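### Protocol 6.10.3 and SAP 5.1 let study exits for adverse-event-type reasons end endpoint follow-up, in conflict with the plan's own continued-follow-up rule; informative censoring is possible, but its size and direction are unknown.

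*SAP*

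**What the plan says.** **Passages that end participation**
- SAP 5.1 (Disposition): "A subject's participation in the study will be discontinued if any of the following applies", followed by adverse event, withdrawn consent, abnormal lab value, lost to follow-up, protocol violation, death and other.
- Protocol 6.10.3 has its own list under the same kind of lead-in. One item is "Subject experiences AEs sufficiently severe to contraindicate continuing the study". The others are consent withdrawal, general condition in the investigator's opinion, refusal to cooperate and a sponsor decision to end the study. The section also allows the investigator to end participation at discretion, and the investigator with the sponsor to withdraw a subject for clinical safety reasons.
- Protocol 6.10.3, 8.1 and 8.2.2.1 describe what happens after withdrawal for an adverse event, abnormal laboratory test or safety reason. The finding is followed until it resolves, is explained or (8.1) is judged permanent. None of the three mentions MACE follow-up.

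**Passages that continue it**
- Protocol 6.10 and SAP 3.4 have subjects who stop study drug complete all remaining visits. In SAP 3.4, stopping assigned drug "or high intensity statin therapy should not result in study discontinuation". SAP 5.1 itself repeats the principle just before its list.
- SAP 8.2 follows every subject to drop-out, death or study closure, and explains drop-out thus: "Drop-out may be due to withdrawal of consent from further data collection or lost to follow-up".
- Subjects without an event are censored at last contact (SAP 8 and 8.2).

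**The concern.** The two sets of passages cannot all be applied as written. A subject whom the investigator withdraws for a severe adverse event leaves the study under protocol 6.10.3. SAP 8.2 assumes that such a subject is still being followed, because neither reason it gives for drop-out covers the case.

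The safeguards do not close this gap. The graded contact options in 6.10.3 are to be offered when the subject asks to withdraw; nothing extends them to exits that the investigator or sponsor initiates. SAP 5.1 keeps early terminators in the analysis and seeks vital status where possible. That recovers deaths but not non-fatal MI or stroke, which are components of the primary endpoint, and event-free time still stops at last contact. None of the three supportive analyses in SAP 8.2 (per-protocol set, undetermined deaths excluded, unstratified test) addresses early exits.

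If such exits differed between arms and were linked to MACE risk, censoring would be informative and the primary hazard ratio biased. The sample-size assumptions in SAP 4.2 give the two arms the same drop-out, 10% by study end, so the design figures do not allow for this.

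**Working it through.** **1. The plan's own figures (SAP 4.2).** The inputs are "Total number of narrowly defined MACE events needed: 250", a hazard ratio of 0.7, two-sided 5% significance and "10.5% event rate in the placebo arm at 18 months", with 7.47% in the active arm.
- Implied hazard ratio: ln(1 − 0.0747)/ln(1 − 0.105) = 0.700.
- Power: Φ(−ln(0.7) × √250/2 − 1.96) = Φ(2.820 − 1.96) = 80.5%, against the stated "approximately 80% power to declare superiority of RVX000222 arm over Placebo".

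The design figures reproduce and are not in dispute.

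**2. Which exits are exposed.**

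| Situation | What the documents provide |
|---|---|
| Drug stopped under the ALT or bilirubin criteria | Stays on the visit schedule to study completion (protocol 6.10.1, SAP 3.8); the note to the synopsis schedule applies the same visits after premature drug discontinuation |
| Subject asks to withdraw | Graded contact options, down to vital-status checks (protocol 6.10.3) |
| Investigator or sponsor withdraws the subject for an adverse event, general condition, non-cooperation or safety | Exit from study; for an adverse event, laboratory or safety reason, follow-up of that finding only; no contact options stated |

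The third row is the gap.

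**3. What it could do to the hazard ratio.** The documents give no exit rate by arm and no MACE risk for those leaving. Everything in this step is therefore assumed.

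Let a fraction f of the active arm leave, with no such exits on placebo, and let leavers have k times the hazard of the rest of their arm. If leavers contribute nothing, the observed ratio is

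HR_obs = HR_true / (1 − f + f·k).

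With HR_true = 1, f = 0.02 and k = 2 this is 1/1.02 = 0.980.

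A fuller calculation counts leavers up to week 8. It uses a placebo hazard of −ln(0.895)/1.5 = 0.0740 per year, 1200 subjects per arm, uniform accrual over 1.7 years, 2.75 years in total and 5% drop-out per year. The error is the chance of a significant result in favour of the drug at 250 events: Φ(−ln(HR_obs) × √250/2 − 1.96). With HR_true = 1.00:

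| f (active arm only) | k | HR_obs | One-sided error |
|---|---|---|---|
| 2% | 2 | 0.982 | Φ(0.144 − 1.96) = 3.5% |
| 2% | 1 | 1.000 | 2.5% |
| 2% | 0.5 | 1.009 | Φ(−0.071 − 1.96) = 2.1% |

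At the design alternative (HR_true = 0.700), f = 2% and k = 2 give 0.688. If f and k are the same in both arms (checked at f = 8%), the ratio stays at its true value.

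**The case against.** The strongest reply is that continued follow-up is the stated design and SAP 5.1 is only loosely worded. The list sits under Disposition and includes death, loss to follow-up and other, which cannot work as rules for removing anyone. The sentence after it speaks of possible reasons. Read literally, any adverse event would remove a subject, which nobody intends. The protocol list has no abnormal-lab or protocol-violation item, and its adverse-event item is confined to severe cases. All of this stands, so the SAP list is best read as reason codes.

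A reader might also infer that, because ALT elevation is the dose-limiting toxicity, liver-related exits would thin out the active arm and favour the drug. The documents do not support that. Subjects who meet the liver criteria stay on the visit schedule. The 7-8% in protocol section 1.0 is the rate of ALT above three times the upper limit of normal. Protocol 6.10.1 responds to values above three and up to five times that limit with monitoring, so 7-8% is not a study-exit rate. Nothing links ALT elevation to MACE risk.

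Finally, SAP 8.2 says drop-out may be due to its two reasons, not that it is confined to them. Analysis is by randomized arm, and exits are tabulated by reason and arm, so an imbalance would be visible.

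What the reply does not answer is protocol 6.10.3. It is an operative conduct rule, it provides for exits that the subject did not request, and it specifies no endpoint follow-up for them. A table of exits shows an imbalance but does not recover missed events.

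**Conclusion.** The inconsistency is real and worth correcting. It matters more in protocol 6.10.3 than in SAP 5.1, because sites act on the protocol. It permits informative censoring of the primary endpoint; it does not establish it. Bias needs two things that the documents do not quantify: unequal exits by arm and a link between exit and MACE risk.

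Under the assumed 2% active-arm exit at twice the hazard, the effect is modest: a null hazard ratio reads as about 0.98 and the one-sided error is about 3.5% instead of 2.5%. It is nil if exit is unrelated to risk, and it runs against the drug if leavers are at lower risk. The stronger conclusions, that the plan biases the result towards the drug or breaks the comparison by randomized arm, do not follow from the text. The 250-event target and the power of about 80% are unaffected.

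**What to change.** 1. **SAP 5.1:** relabel the list as recorded reasons, tabulated separately for stopping study drug and for leaving the study.
2. **SAP 5.1 and protocol 6.10.3:** reconcile both with SAP 8.2 by stating that endpoint and vital-status follow-up ends only with death, full withdrawal of consent, loss to follow-up or study closure.
3. **Protocol 6.10.3:** extend the existing contact options to investigator- and sponsor-initiated exits, so that non-fatal MI and stroke are still sought in these subjects.

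The cost is SAP wording, a clarification in the next protocol amendment and a note to sites. No treatment or stopping rule, event target or test changes.

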5.2. Significant Protocol Deviations

The Investigator will not deviate from the protocol without prior written approval from Sponsor or its designee, except in medical emergencies. In the instances that protocol deviations do occur, these will be documented and reviewed as stated in generation of the per-protocol set and displayed. The list of major protocol violations is expected to be as follows:

- Patients who had only an elective PCI (percutaneous coronary intervention) as their index event instead of an urgent one that was performed for the presentation of unstable angina or myocardial infarction
- Acute Coronary Syndrome outside the protocol-specified window
- No evidence of T2DM Diabetes recorded in the case report forms
- Use of immunosuppressants as identified in the exclusion criteria of the protocol and other clinical documentation.

6. Demographics and Other Baseline Characteristics

6.1. Demographics

Baseline and demographic information will be summarized for each treatment group and overall. Demographic and baseline characteristics are age in years, age categories (≤ 65 vs >65 and by quartiles), sex, race, country, height (cm), weight (kg), and body mass index (BMI) (kg/m^2). Summaries of demographic and baseline characteristics will be based on the FAS. No inferential statistics will be presented.

For subjects not in the United States, age in years will be collected directly from the eCRF. Otherwise, age will be calculated as the integer part of

$$\frac{(\text{date of informed consent} - \text{date of birth} + 1)}{365.25}$$

and will be summarized using descriptive statistics. The numbers and percentages of subjects in 2 age categories (≤ 65 vs >65) and by quartiles will also be reported.

The number and percentage of male and female subjects will be summarized.

The number and percentage of subjects in each race category (American Indian or Alaska Native, Asian, Black or African American, Native Hawaiian or Other, Pacific Islander, White and Other) will be presented.

Height will be measured at screening only. Weight will be measured during each physical examination. BMI will be calculated using weight and height collected at Screening as follows:

$$\frac{\text{weight in kg}}{((\text{height in cm}) / 100)^2}$$

Height, weight, and BMI at Baseline will be summarized using descriptive statistics.

6.2. Baseline Disease Characteristics and Medical History

Baseline disease characteristics such as time since diagnosis of T2DM to randomization, index ACS event type, and time from ACS to randomization will be calculated or extracted from medical history and presented by treatment group.

Medical history will consist of any significant conditions or diseases that stopped at or prior to the date of informed consent. Ongoing conditions will be considered concurrent medical conditions.

Concurrent medical conditions are significant ongoing conditions or diseases present at time of informed consent. These include clinically significant laboratory findings, ECG, or physical examination abnormalities. Summaries of medical history and concurrent medical conditions will be based on the FAS.

Medical history and concurrent medical conditions will be coded using the latest possible version of Medical Dictionary for Drug Regulatory Activities (MedDRA).

7. Treatments and Medications

7.1. Study Treatments

7.1.1. Study Drug Exposure

RVX000222 or matching placebo will be taken orally with meals in the morning and in the evening, 10-12 hours apart.

Table 2: Study Drug Administration Schedule

Treatment Group	Daily dose (mg)	Dose administration b.i.d. (mg)	AM Dose (mg)	PM Dose (mg)	No. of capsules/day
A: RVX000222	200	100	100	100	2
B: Placebo	0	0	0	0	2

As described in [section 3.8](#), if subjects have elevated ALT values they may be administered study drug or matching placebo at a reduced dose of 50 mg b.i.d. This dose change information is to be collected in the eCRF as action taken with study drug when reporting elevated ALT values as an adverse event and subject to confirmation by the medical monitor. Subjects with at least one study treatment dose reduction and those with none will be represented by treatment group on FAS. Information on number of subjects by number of dose reductions will also be summarized by treatment group.

Study drug exposure will begin on the day of the first dose of study drug and end on the day of the last dose of study drug. Duration of study drug exposure in months will be defined as (date of last dose - date of first dose + 1)/30.4.

Study participation will begin on the day of randomization and end on the day of last contact. Duration of study participation in months will be defined as (date of last contact – date of randomization +1)/30.4.

Duration of exposure to study drug and duration of study participation will be summarized for the FAS using descriptive statistics. Duration of study drug exposure and duration of study participation will also be categorically summarized by number and percentage of subjects who had at least 12-weeks, greater than 12 weeks up to 24 weeks, greater than 24 weeks up to 52 weeks, and greater than 52 weeks of study drug exposure and study participation. Duration of drug exposure on subjects with at least one dose reduction will be summarized by the aforementioned categories.

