Overall, RVX000222 was generally well tolerated and AEs were mild with little discernible difference between placebo- and the RVX000222-treated subjects. The dose-limiting toxicity for RVX000222 is a generally non-symptomatic elevation in serum transaminases (alanine aminotransferase [ALT] and in some cases aspartate aminotransferase [AST]), without adversely affecting total bilirubin values in any subject. There was no increase in alkaline phosphatase (ALP) observed. There was an overall incidence of 7-8% of subjects with ALT >3x the upper limit of normal range (ULN). There was often confounding with use of drugs known to increase ALT (diclofenac and clavulanic acid) or prior history of hepatitis. Raised enzymes return promptly to within the normal transaminase range (approximately 15 days for ALT >5xULN), suggesting that any hepatocellular effect can be reversed by suspending treatment with investigational drug. For subjects with elevations >3xULN and <5xULN, treatment was continued and all returned to normal levels. Subjects with ALT elevations >5x and <8xULN were dose interrupted, re-challenged at a lower dose and the majority successfully completed the studies. Drug-induced ALT elevations >3xULN were observed between weeks 4-12 across all 4 completed Phase 2 trials, with one exception. One subject with elevated ALT and AST at Week 20 due to cholecystitis was noted in RVX222-CS-007. No cases of Hy's Law have been detected.

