Central Laboratory:																						
Physical Exam	x																					
Fasting Lipid profile	x																					
Central Laboratory:																						
Hematology, HbA1c	x																					
Fasting Lipid profile	x																					
Chemistry	x																					
Hematology, HbA1c	x																					
Chemistry	x																					
Urinalysis	x																					
Chemistry	x																					
Hepatitis Serology	x																					
Urinalysis	x																					
Liver Safety Panel	x	x	x	x	x	x	x	x	x	x	x	x	x	x	x	x	x	x	x	x	x	x
Biomarker Laboratory Tests																						
Lipoproteins, fasting insulin		x										x					x			x		x
Inflammation Panel		x															x					
Serum/Plasma Archive		x															x					
Pharmacogenomic		x			x																	
MOCA		x																				x
EQ-5D-5L		x																				x
Adverse Events	x	x	x	x	x	x	x	x	x	x	x	x	x	x	x	x	x	x	x	x	x	x
Prior / Con. Medication	x	x	x	x	x	x	x	x	x	x	x	x	x	x	x	x	x	x	x	x	x	x
Drug Dispense/Account.	x	x	x	x	x	x	x	x	x	x	x	x	x	x	x	x	x	x	x	x	x	x

Table 1) until study completion.

If the ALT or serum bilirubin elevation has a likely cause other than investigational drug (e.g. trauma, infection-inflammation, surgery, acetaminophen, clavulanic acid, diclofenac) investigational drug may be restarted at 50 mg b.i.d. once ALT returns to 1.5 xULN. Subjects should continue with all scheduled study visits according to the Schedule of Events (

Hepatitis Serology	x																	
Liver Safety Panel	x	x	x	x	x	x	x	x	x	x	x	x	x	x	x	x	x	x
Biomarker Laboratory Tests																		
Lipoproteins, fasting insulin		x								x			x		x			x
Inflammation Panel		x						x					x					
Serum/Plasma Archive		x						x					x					
Pharmacogenomic		x			x													
MOCA		x											x					x
EQ-5D-5L		x									x		x		x			x
Adverse Events	x	x	x	x	x	x	x	x	x	x	x	x	x	x	x	x	x	x
Prior / Con. Medication	x	x	x	x	x	x	x	x	x	x	x	x	x	x	x	x	x	x
Drug Dispense/Account.	x	x	x	x	x	x	x	x	x	x	x	x	x	x	x	x	x	x

Table 1) and will have additional liver safety panel tests drawn according to the original study schedule:

- Weeks 0-12 after investigational drug is reinitiated: liver safety panel every 2 weeks (Weeks 0, 2, 4, 6, 8, 10, 12 after re-initiation)
- Weeks 12-28 after investigational drug is reinitiated: liver safety panel every 4 weeks (Weeks 16, 20, 24 after re-initiation)

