4.1. Reporting Conventions and Dates Handling

Derived analysis data sets will be produced from the electronic case report form (eCRF) data, central laboratory data and the electronic adjudication data (EAS) to assist with analysis and summary of both efficacy and safety endpoints. Derived data sets will identify observations selected according to the study window convention described in [section 4.5](#) and values that will be summarized.

The number and percentage of subjects will be used to summarize categorical variables. When count data are presented and the count is zero, the percentage will be suppressed. Unless otherwise specified, the denominator for percentages will be the number of subjects in a given treatment group within the analysis set of interest. Descriptive statistics (number of subjects with non-missing values, mean, standard deviation, minimum, 25th percentile, median, 75th percentile, and maximum) will be used to summarize continuous variables unless otherwise noted.

In summary tables for categorical data, all categories will be presented if they are specified on the eCRF (eg, discontinuation reason), or if categories are ordered intervals (eg, age groups), regardless of whether or not a subject is found in a given category. For other categorical data (eg, AEs and medications), only categories with at least 1 subject will be presented. A row denoted “Missing” will be included in count tabulations where specified on the shells to account for dropouts and missing values. When no data are available for a table or listing, an empty page with the title will be produced with suitable text (eg, “There are no observations for this table/listing.”).

Means and percentiles will be presented to 1 more decimal place than the recorded data. Standard deviations and standard errors will be presented to 2 more decimal places than the recorded data. Minimum and maximum values will be presented using the same number of decimal places as the recorded data. Percentages will be presented to 1 decimal place. Hazard ratios will be presented with 3 decimal places. Confidence intervals (CIs) will be presented using the same number of decimal places as the parameter estimate (eg, LS mean or hazard ratio).

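### The first exposure category in SAP 7.1.1 contains the other three and leaves no row for under 12 weeks, probably a slip for up to 12 weeks

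*SAP*

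**What the plan says.** SAP 7.1.1 plans two summaries of duration. The first is continuous: "Duration of exposure to study drug and duration of study participation will be summarized for the FAS using descriptive statistics". By SAP 4.1, such statistics include the "mean, standard deviation, minimum, 25th percentile, median, 75th percentile, and maximum". The second is categorical, with four categories: "at least 12-weeks, greater than 12 weeks up to 24 weeks, greater than 24 weeks up to 52 weeks, and greater than 52 weeks". These apply to both drug exposure and study participation. They are then carried over to a subset: "Duration of drug exposure on subjects with at least one dose reduction will be summarized by the aforementioned categories".

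Under SAP 4.1, unless otherwise specified, the "denominator for percentages will be the number of subjects in a given treatment group within the analysis set of interest".

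On the source of dose changes, SAP 7.1.1 says that "dose change information is to be collected in the eCRF as action taken with study drug when reporting elevated ALT values as an adverse event". It then plans counts of subjects with and without a reduction, and of subjects by number of reductions. SAP 3.8 and Protocol 6.5 link the reduced dose to ALT elevation. Protocol 6.10.1 words the condition for restarting at the reduced dose more widely: "If the ALT or serum bilirubin elevation has a likely cause other than investigational drug".

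Protocol section 1.0 describes transaminase elevation as the dose-limiting toxicity and gives its timing in the Phase 2 trials: "Drug-induced ALT elevations >3xULN were observed between weeks 4-12", with one exception, at week 20.

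**The concern.** A table of durations should place each subject in exactly one row. Here the first row is open-ended upwards and so includes everyone in the three rows below it, while short durations have no row.

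The missing range is the one of most interest for liver safety, because it includes weeks 4 to 12. Protocol 4.0 keeps all surviving subjects in follow-up for at least 24 weeks from randomization. Exposure below 12 weeks should therefore come almost entirely from early stopping, death or drop-out, and hardly ever from study closure. A programmer who follows the SAP literally would produce a table without a row for that group.

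The dose-change sentence raises a lesser question. It names only ALT events as the place where a change is recorded, while Protocol 6.10.1 also allows a reduced-dose restart after a bilirubin elevation. The SAP does not say from what source such a reduction would be counted.

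**Working it through.** The point concerns category definitions, so the plan has no stated figure to reproduce.

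**Step 1: assign durations to rows.** Inputs are the four categories in SAP 7.1.1 and the conversion weeks = days/7 from SAP 4.5. The boundary is 12 × 7 = 84 days.

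| Duration (days) | Rows as written | Rows if the first is 12 weeks or less |
|---|---|---|
| 1, 28, 56, 83 | none | first only |
| 84 | first only | first only |
| 85, 168 | first and second | second only |
| 169, 364 | first and third | third only |
| 365, 700 | first and fourth | fourth only |

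As written, every tested duration below 84 days has no row and every one from 85 days has two. With the first row read as 12 weeks or less, each tested duration has exactly one row and the rows add to 100%.

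**Step 2: effect on an exposure table.** The SAP plans about 2400 subjects at 1:1, hence 2400/2 = 1200 per arm. The documents give no rate of stopping drug before week 12, so the share s is an assumption, shown over a range. Nobody is assumed to have exactly 84 days. Then:

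- subjects without a row = 1200 × s
- first row = 1200 × (1 − s)
- sum of the four rows = 2 × (1 − s) of the arm

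| Assumed s | No row | First row | Sum of rows | Arm size minus first row |
|---|---|---|---|---|
| 2% | 24 | 1176 | 196% | 24 |
| 5% | 60 | 1140 | 190% | 60 |
| 8% | 96 | 1104 | 184% | 96 |
| 10% | 120 | 1080 | 180% | 120 |

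The last column shows that the missing count can be recovered by subtraction.

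**Step 3: effect on the participation table.** The sample size section assumes 5% drop-out per arm by year one. With a constant hazard, drop-out by week 12 is 1 − 0.95^(12/52) = 0.0118, and 0.0118 × 2400 ≈ 28 subjects over both arms. These would have no participation row. This is study drop-out and says nothing about stopping for liver toxicity.

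**Step 4: source of dose changes.** Protocol 8.2.2 lists action taken with investigational drug among the items recorded for every adverse event. It also makes an adverse event of any laboratory value that leads to interruption or discontinuation. The data for a full count are therefore collected. What the SAP lacks is a statement that the count uses them.

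**The case against.** The strongest reply is that this is a slip of the pen and that little is lost. The other three categories run on without a gap from just above 12 weeks, so the first was very probably meant to be 12 weeks or less. The table shells, which SAP 4.1 mentions and which are not part of these documents, may already have it right. This stands, and it is why the point is minor. The SAP text is still the instruction that a programmer follows.

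A reader might infer that early stoppers disappear from the report. The documents do not support that. The denominator is the whole arm, so their number is the arm size minus the first row. In the dose-reduced subset it is the number with a reduction, which is also reported, minus the first row. Early stoppers also enter the continuous summary, the disposition table (SAP 5.1) and the table of adverse events leading to drug withdrawal (SAP 9.1.6). These are only partial substitutes. Neither of the last two tables is specified by time. A stopping share of 10% or less would lie below the 25th percentile, so the continuous summary would not count it.

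A reader might also infer that dose changes are captured only through ALT events and that reductions will be undercounted. That is not established. Action taken is recorded for all adverse events, and the counting sentence in SAP 7.1.1 is not limited to ALT. The bilirubin route may also be rare, since Protocol section 1.0 reports no adverse effect on total bilirubin in any earlier subject.

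Finally, the 7-8% in Protocol section 1.0 must not be read as a stopping rate. It is the incidence of ALT above three times the upper limit. Subjects between three and five times the limit continued treatment. Those between five and eight times were interrupted and restarted at a lower dose, and most of them completed.

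**Conclusion.** The point holds in a limited form. The four categories in SAP 7.1.1 are neither mutually exclusive nor exhaustive. They give no row to the period that includes the known ALT window, and the defect carries over to study participation and to dose-reduced subjects. What is lost is a printed count by arm for the first 12 weeks, together with rows that add to 100%. The count itself survives by subtraction.

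This is wrong as written and minor. It affects safety reporting only and leaves the primary analysis, alpha and power untouched. The finding on the categories follows from their wording and needs no assumption. The 24 to 120 subjects per arm rest on an assumed 2% to 10% stopping before week 12, and the 28 in the participation table on the planned drop-out at a constant hazard.

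The dose-change part is a secondary point of missing detail: the source of the count is not stated, and the passages on ALT and on ALT or bilirubin do not agree.

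**What to change.** In SAP 7.1.1, change the first category to up to 12 weeks and keep the other three. State that the same rows apply to drug exposure, study participation and the dose-reduced subset, and check that the table shell agrees.

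Secondary: add one sentence that dose reductions are counted from the action-taken field of any adverse event, which Protocol 8.2.2 already collects. Reconcile SAP 3.8, SAP 7.1.1 and Protocol 6.5 with Protocol 6.10.1 on which laboratory elevations the reduced-dose provision covers. Which rule applies is for the sponsor's clinical team to settle.

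The cost is one corrected label, one added sentence, a check of the shell and a consistency edit. No new data are needed, and the changes should be made before unblinding.
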